5.3 Modification of Diet and Glucose Control

Brief dietary counseling reflecting the current standard of care will be provided to all subjects including low potassium diet in subjects with CKD.

For subjects with T2DM entering the study, the PI will evaluate the subject's current diet, diabetes treatment regimen and glucose monitoring regimen with the subject prior to Randomization to determine whether modification of any of these are required in view of the potential initiation of dapagliflozin.

For subjects who are on insulin treatment and/or metformin and are prone to hypoglycemic events based on the subject's medical history, additional glucose monitoring should be incorporated into their standard of care as determined by the PI and if clinically indicated.

5.4 Lifestyle Considerations

5.4.1. Caffeine, Alcohol, and Tobacco

Subjects will abstain from ingesting caffeine or xanthine-containing products (e.g., coffee, tea, cola drinks, and chocolate) for at least 30 minutes before the start of any study-related BP measurement.

Subjects will abstain from alcohol for at least 30 minutes before the start of any study-related BP measurement.

Subjects will abstain from smoking and the use of cannabis-derived or nicotine-containing products (including nicotine patches, gums, and e-cigarettes) for at least 30 minutes before the start of any study-related BP measurement.

5.4.2. Activity/Exercise

Subjects will abstain from strenuous exercise for at least 30 minutes before the start of any study-related BP measurement and for 24 hours before each blood collection for clinical laboratory tests. Subjects may participate in light recreational activities (e.g., watching television, reading).

6. STUDY DRUG ADMINISTRATION AND MANAGEMENT

The study drug products for this study are lorundrostat as well as the matching placebo. Additionally, commercially available dapagliflozin will be provided to SGLT2i naïve subjects or those that wish to switch to study provided SGLT2i. Subjects may also choose to stay on their currently prescribed SGLT2i.

The formulation and the manufacturing of study drug follows generally accepted standard procedures. The description, covering in detail all aspects regarding quality and safety of study drug product is part of the Investigator's Brochure (IB) for lorundrostat and product prescribing information for dapagliflozin (FARXIGA®) (FDA Reference ID: 4788803).

■ [REDACTED]

[REDACTED]
[REDACTED]
[REDACTED]
[REDACTED]

[REDACTED]

[REDACTED]	[REDACTED]	[REDACTED]
[REDACTED]	[REDACTED]	[REDACTED]
[REDACTED]	[REDACTED] [REDACTED] [REDACTED] [REDACTED]	[REDACTED]
[REDACTED]	[REDACTED] [REDACTED]	[REDACTED] [REDACTED] [REDACTED] [REDACTED]
[REDACTED]	[REDACTED] [REDACTED] [REDACTED] [REDACTED]	[REDACTED]
[REDACTED]	[REDACTED] [REDACTED] [REDACTED]	[REDACTED] [REDACTED] [REDACTED] [REDACTED]
[REDACTED]	[REDACTED]	[REDACTED]
[REDACTED]	[REDACTED]	[REDACTED]
[REDACTED]	[REDACTED] [REDACTED] [REDACTED]	[REDACTED]

Abbreviations: HBr, monohydrobormide; IMP, investigational medicinal product; QD, once daily.

All packaged tablets will be assigned a unique identifying number, used by the Randomization and trial supply management (RTSM) system to identify the content but maintaining the blind. The test materials will be identified by the lot, batch numbers, retest date, and certificate of analysis.

6.2 Dosing and Administration

During the study all subjects will take the same number of tablets, regardless of treatment allocation, to maintain the blind. Subjects will be instructed to take the tablets orally QD at approximately the same time each morning.

6.3 Preparation, Handling, Storage, Accountability

6.3.1. Study Drug Preparation

Not applicable.

6.3.2. Study Drug Packaging and Labeling

Study drug will be labelled, packed, and released in accordance with all applicable laws, regulations, and administrative provisions relating to the implementation of good manufacturing practice and good clinical practice in the conduct of clinical trials on medicinal products for human use.

Lorundrostat and matching placebo tablets are packaged in 30 count 60 cc white round high density polyethylene bottles with a child-resistant cap. As the study is a DB study, labeling of the lorundrostat and matching placebo tablets/capsules packaging will not show the treatment allocation. All other information required by regulation will appear on the label.

6.3.3. Study Drug Handling and Disposal

All study drug supplies are to be used only for this clinical study and not for any other purpose. Authorized study personnel must maintain a full record of study drug disposition (i.e., a log by date received, dispensation date and subject, date of return from the subject, and detailed study drug usage by each study subject).

After reconciliation, used study drug will be handled according to instructions provided by the Sponsor. At study conclusion, all remaining unused supplies will be similarly handled. Authorized study personnel will record any unaccounted supplies in the final accountability records.

6.3.4. Study Drug Storage

The study drugs should be stored at room temperature (59°F to 77°F [15°C to 25°C]) in an approved storage area with access limited to authorized study personnel.

6.3.5. Study Drug Accountability

Study drugs (including placebo) will be maintained under adequate security by appropriate site personnel (e.g., pharmacist) and in accordance with applicable regulatory requirements. Study drugs remaining at the end of the study will be returned to the Sponsor or their representative or destroyed on behalf of the Sponsor.

The Investigator or designee must maintain adequate records of receipt and distribution of all study drug, using appropriate accountability records.

Subjects will be randomized (1:1) to two treatment sequences: LP and PL. Randomization sequence numbers and study drug supplies will be assigned using RTSM. Access to the Randomization sequence codes will be controlled and documented.

Except when it is essential for the medical management of the subject, unblinding the treatment assignment will be considered a protocol deviation. Emergency treatment allocation information will be available by secured access to the RTSM system. If possible, the Investigator should contact the Sponsor before unblinding any subject's treatment assignment. If this is not possible, the Sponsor should be notified within 24 hours after the unblinding event. After unblinding, the subject will be discontinued from study drug treatment, but will continue participation in the study, including participation in all remaining visits and assessments, until the EoS visit. The reason for unblinding must be documented in the eCRF.

Compliance with study drug dosing will be assessed at each visit. Compliance will be assessed by direct questioning and counting returned tablets during the site visits and will be documented in the source documents and relevant case report form. Deviation(s) from the dosage regimen should be recorded.

A record of the quantity of study drug dispensed to and administered by each subject must be maintained and reconciled with study intervention and compliance records. Study drug start and stop dates, including dates for study drug holds and/or dose reductions will also be recorded.

Study drug compliance will be defined by the treatment compliance ratio: The number of doses taken by the subject divided by the number of doses dispensed. Compliance is defined as taking between 75% and 125% of the study drug provided.

This study may use a medication adherence monitoring platform. The platform will be provided on a smartphone application. Built-in reminders and a communication system allow real-time intervention in case of missed doses, reinforce the proper dosing schedule, and improve data integrity.

[REDACTED]

[REDACTED]

[REDACTED]

[REDACTED]

[REDACTED]

If, at any time during the study, a subject experiences a clinically significant laboratory or medical assessment (e.g., hyperkalemia, hyponatremia, symptomatic hypotension, severely elevated BP,

hypercortisolemia, hypocortisolemia, reduction in kidney function), laboratory test results will be confirmed using a local laboratory and AOBP measurements will be repeated. At the discretion of the Investigator, in consultation with the Medical Monitor, the dose of the study drug may be modified, or temporarily or permanently discontinued. The Investigator may temporarily interrupt study drug without prior consultation with the Medical Monitor at their discretion and discuss their decision and whether the interruption should be converted to a discontinuation with the Medical Monitor within 24 hours. A subject with modification of their study drug will not be withdrawn from the study.

6.8 Concomitant Therapy

Any medication or vaccine (including over the counter or prescription medicines, recreational drugs, vitamins, and/or herbal supplements) that the subject is taking at Screening or takes during the study must be recorded along with:

- Reason for use
- Dates of administration including start and end dates
- Dosage information including dose and frequency

6.9 Prohibited Treatments

The following medications are prohibited from the Screening Visits until the End of Treatment (EOT), unless otherwise stated:

- Previous treatment with lorundrostat or other ASI within 4 weeks or 5 half-lives (whichever is longer) prior to the Screening Visit.
- Use of ENaC inhibitors or MRAs, including, but not limited to amiloride, triamterene, spironolactone, eplerenone, finerenone, from 4 weeks prior to the Screening Visit and during study participation. With the exception of MRAs in primary aldosteronism.
- Use of anti-hypertensive medications (AHT) medications other than lorundrostat and those already prescribed at the Screening Visit, for the duration of study participation, require approval of the Investigator, followed by reporting to the Medical Monitor. Consultation with the Medical Monitor is recommended.
- Sympathomimetic decongestants on the morning of any study-related BP assessment.
- Chronically administered oral corticosteroids from 3 months prior to the Screening Visit and during study participation. Short-term (i.e., ≤ 2 weeks) use of topical corticosteroids is allowed if taken for ≥ 1 month prior to Randomization. Intramuscular steroids from 3 months prior to the Screening visit until completion of study participation. Inhaled and intra-ocular corticosteroids are allowed.
- Short-acting nitrates taken for angina or for underlying cardiac disease during study participation are allowed but should be monitored and study drug discontinued if symptoms of hypotension or orthostatic hypertension occur or SBP < 110 mmHg is documented. Chronic, long-acting doses of nitrates are acceptable.
- Enrollment of subjects requiring treatment with strong CYP3A and CYP3A4 inducers (e.g., apalutamide, carbamazepine, enzalutamide, fosphenytoin, lumacaftor, mitotane, phenobarbital,

phenytoin, primidone, rifampin, St. John's Wort) must be approved by the Medical Monitor. Moderate inducers of CYP3A and CYP3A4 are acceptable.

- Use of Proton Pump Inhibitors (PPIs) for more than 3 days per week. These must be abstained for at least 5 days prior to a scheduled visit.
- Use of digoxin is allowed, but levels should be monitored.

The decision to administer a prohibited medication/treatment during the study period is done with the safety of the subject as the primary consideration. Consult with the Medical Monitor for continued evaluation of study eligibility.

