2.3.1.3. Risk of Hypotension and Dizziness

In healthy subjects, the incidence of dizziness/postural dizziness was slightly higher among lorundrostat treated subjects compared to placebo subjects.

Furthermore, hypotension with symptoms was seen in [REDACTED] who received lorundrostat in the Phase 2 study of subjects with uncontrolled hypertension (MLS-101-201). These events were

reversible with treatment cessation as expected based on the mechanism of action of lorundrostat. In addition, 3 subjects developed orthostatic hypotension in the absence of seated hypotension, defined as a fall of 20 mmHg in systolic BP (SBP) or 10 mmHg in diastolic BP (DBP) when going from sitting to standing position. In each case, the hypotensive episode resolved spontaneously and did not recur for the remainder of the treatment period. Two of these events were assessed by the Investigator as unlikely to be related to study medication; one event was assessed as possibly related.

Subject BP, in both seated and standing positions, will be regularly assessed throughout the course of this study. Investigators will be instructed to treat hypotensive episodes in accordance with the standard of care at the site/institution and medical guidelines.

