3.2.3. Safety Endpoints

- Incidence and severity of AEs
- Clinically significant changes in vital signs (body temperature, heart rate, and respiratory rate), physical examination and ECG parameters
- Clinically significant changes in clinical laboratory assessments (hematology, chemistry, and urinalysis)
- Incidence of AEs of Special Interest (AESI)
 - Modification of study drug dose due to hyperkalemia (e.g., dose reduction, dose hold, or permanent dose discontinuation)
 - Modification of study drug dose due to hyponatremia (e.g., dose reduction, dose hold, or permanent dose discontinuation)
 - Hypotension with symptoms (e.g., light-headedness, dizziness, presyncope, or syncope)
 - Severely elevated BP (AOBP SBP >180 mmHg or AOBP DBP >110 mmHg)
 - Modification of study drug dose due to hypercortisolism (morning serum cortisol >35 µg/dL, confirmed by 24-hour urinary free cortisol)
 - Discontinuation of study drug due to hypocortisolism confirmed by ACTH stimulation test
 - Overdose of study drug

- Modification of study drug dose due to reduction in kidney function (e.g., dose reduction, dose hold, or permanent dose discontinuation)

■

■

■

■

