5.2 Exclusion Criteria

Subjects meeting any of the following criteria are **not** eligible for inclusion in this study:

1. Women who are pregnant, plan to become pregnant, or are breast-feeding
2. Subjects with known hypersensitivity to lorundrostat or any of its respective excipients
3. Subjects with known hypersensitivity to dapagliflozin or any of its respective excipients (subjects beginning dapagliflozin only)
4. Treatment, or anticipated treatment, with any prohibited medication within the timeframes described in [Section 6.9](#) of this protocol.
5. Treatment, or anticipated treatment, with triamterene and amiloride
6. Participation in a trial involving an investigational device or drug within 4 weeks or 5 half-lives (whichever is longer) prior to the Screening Visit
7. Previous treatment with lorundrostat or other ASI within 4 weeks or 5 half-lives (whichever is longer) prior to the Screening Visit

8. At Screening, serum potassium >5.0 mmol/L
9. At Randomization, serum potassium >5.0 mmol/L (prior to first dosing of study drug)
10. At Screening, serum sodium <135 mmol/L (corrected for hyperglycemia using the Katz formula). Rescreening of subjects with an exclusionary serum sodium is only allowed if two consecutive measurements at least one week apart are ≥ 135 mmol/L
11. Total bilirubin $>2\times$ upper limit of normal (ULN) except for those with a diagnosis of Gilbert's syndrome, unless approved by Medical Monitor
12. History of clinically significant hyponatremia within 1 year prior to Screening
13. History of adrenal insufficiency or an abnormal ACTH stimulation test within 1 year prior to Screening
14. Hospitalization for the treatment of urgent or emergent hypertension within 1 year prior to Screening
15. Current, known or presumed white coat hypertension/significant white coat effect (as defined in the SRM)
16. Current, known or presumed orthostatic hypotension
17. Current, known or presumed autonomic dysfunction
18. Arm circumference >55 centimeters at Screening
19. Subjects with a previously proven secondary cause of hypertension are excluded with the following exceptions:
 - a. Subjects with documented sleep apnea are eligible to participate
 - b. Subjects with documented primary hyperaldosteronism are eligible to participate if they discontinue use of a MRA. They should have <20 mmHg increase in AOBP SBP, and AOBP SBP <150 mmHg at Randomization. MRA treatment may be tapered over a one-week period.

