8.4.7.3. Symptomatic and Asymptomatic Hypotension

If subjects experience symptoms of hypotension (e.g., light-headedness, dizziness, presyncope, or syncope) during the study, it will be medically managed by the Investigator in communication with the Medical Monitor. Dose reduction of study drug according to the instructions in the SRM may be considered.

In cases of hypotension without symptoms (AOBP DBP [REDACTED] 5 [REDACTED], or DBP between [REDACTED] 5 [REDACTED] <85 mmHg plus AOBP SBP [REDACTED]), the lorundrostat dose should be reduced first. If a subject experiences symptoms of hypotension (e.g., frequent light headedness, pre-syncope, dizziness) but does not meet the above defined BP threshold for hypotension, the study drug dose should be reduced. Dose reduction of the study drug is the first step. If symptoms and/or BP thresholds persist following dose reduction, the subject may be discontinued from study drug in consultation with the Medical Monitor.

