8.4.7.4. Severely Elevated Blood Pressure

Subjects with systolic AOBP of [REDACTED] or diastolic AOBP of [REDACTED] will have any prescribed AHT regimen adjusted as described in the SRM. If additional medications are needed, doxazosin 1 mg is recommended, but medication additions are performed at the Investigator's discretion in consultation with the Medical Monitor.

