8.4.7.6. Hypocortisolism

Subjects will have their serum cortisol measured as per the schedule of assessments, with the blood draw performed as close to 8 AM as possible.

- Any subject with a morning serum cortisol [REDACTED] will undergo an ACTH stimulation test within 1 week of the result being known.
- Any subject with morning serum cortisol [REDACTED] L accompanied by ≥ 2 signs and symptoms of adrenal insufficiency (i.e., weakness, loss of appetite, unintentional weight loss, hyponatremia, hypoglycemia) plus clinical findings of orthostatic hypotension, pre-syncope, or syncope, will undergo an ACTH stimulation test within 48 hours of the result being known.
 - If associated with a concurrent acute illness, including COVID-19, the ACTH stimulation test timing will be at the discretion of Investigator but may be delayed for no more than 5 days from the morning serum cortisol result being known.
- Any subject with morning serum cortisol [REDACTED] L accompanied by ≥ 2 [REDACTED] and symptoms of adrenal insufficiency but no BP or laboratory abnormalities, will undergo an ACTH stimulation test within 1 week of the result being known.
- Any subject with morning serum cortisol [REDACTED] accompanied by asymptomatic orthostatic hypotension with hypoglycemia or hyponatremia will undergo an ACTH stimulation test within 1 week of the result being known.
- Any subject with an ACTH test result diagnostic of adrenal insufficiency will immediately discontinue study drug and will be referred to specialized care (e.g., endocrinologist/urgent care) for further management. The subject is not required to withdraw from the study in such cases.

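### Protocol 6.9 tells sites to stop study drug in short-acting nitrate users for orthostatic hypertension, almost certainly a slip for orthostatic hypotension; a low-severity wording correction to a safety rule

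*Protocol*

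**What the plan says.** Protocol 6.9 lists short-acting nitrates, taken for angina or underlying cardiac disease, as allowed with a condition: users "should be monitored and study drug discontinued if symptoms of hypotension or orthostatic hypertension occur or SBP < 110 mmHg is documented". This tells sites when to stop study drug; it is not background text.

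Elsewhere the protocol deals with orthostatic and high blood pressure as follows.

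- Entry: exclusion criterion 16 (5.2, repeated in the synopsis) is "Current, known or presumed orthostatic hypotension".
- Known risk: 2.3.1.3 reports that in the earlier Phase 2 study "3 subjects developed orthostatic hypotension in the absence of seated hypotension", and defines the condition as a fall of 20 mmHg systolic or 10 mmHg diastolic from sitting to standing.
- Hypocortisolism (8.4.7.6): one rule requires an ACTH test when low cortisol and symptoms come with findings that include orthostatic hypotension. Another applies when low cortisol is "accompanied by asymptomatic orthostatic hypotension with hypoglycemia or hyponatremia will undergo an ACTH stimulation test".
- Hypotension without symptoms (8.4.7.3): at partly redacted thresholds, "the lorundrostat dose should be reduced first".
- High pressure: 3.2.3 lists as an event of special interest "Severely elevated BP (AOBP SBP >180 mmHg or AOBP DBP >110 mmHg". Under 8.4.7.4, subjects with severely elevated pressure "will have any prescribed AHT regimen adjusted as described in the SRM".
- General dose modification (the text just before 6.8, whose heading is redacted and which 7.1 cites as 6.7): for a list of events that includes severely elevated BP, study drug may be modified or stopped at the Investigator's discretion in consultation with the Medical Monitor. It adds that "The Investigator may temporarily interrupt study drug without prior consultation with the Medical Monitor at their discretion".

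**The concern.** The rule protects people who take a nitrate on top of a drug being tested for lowering blood pressure. The hazard to guard against there is pressure that falls too far. A rise in pressure on standing does not belong in that list, and nothing in the protocol explains why it would be there.

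Read literally, the sentence stops study drug for a postural rise and does not name a postural fall. Section 8 allows no waivers and has deviations from study conduct recorded, so sites and monitors are expected to follow the wording. The trigger can also be applied in practice: Table 1 schedules seated and standing AOBP at every visit except Run-in, and 8.2.3 has the orthostatic change calculated and recorded.

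**Working it through.** No formula applies and the plan states no figure on this point. The check compares texts.

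**1. The sentence itself.** It has three triggers:

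- symptoms of hypotension: low pressure
- orthostatic hypertension: high pressure
- SBP < 110 mmHg documented: low pressure

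That is 2 low and 1 high.

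**2. Use of the term elsewhere.** Mentions of an orthostatic condition in the visible protocol text:

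| Place | Condition | Mentions |
|---|---|---|
| Synopsis, exclusion 16 | hypotension | 1 |
| 2.3.1.3 | hypotension | 1 |
| 5.2, exclusion 16 | hypotension | 1 |
| 8.4.7.6 | hypotension | 2 |
| 6.9 | hypertension | 1 |

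Hypotension: 1 + 1 + 1 + 2 = 5. Hypertension: 1. The synopsis and 5.2 repeat one criterion, so the five mentions come from three separate contexts: eligibility, known risk and hypocortisolism. All three agree. Orthostatic hypertension is not defined in either document.

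**3. How high pressure is handled.** For severely elevated pressure (above 180 mmHg systolic or 110 mmHg diastolic in 3.2.3), 8.4.7.4 directs adjustment of the antihypertensive regimen and does not order a stop. The dose-modification text permits stopping for the same event, but only by discretion. Taken literally, 6.9 would direct a stop for an orthostatic rise of unstated size, which is stricter than the protocol's response to a systolic pressure above 180 mmHg. This supports the reading as a slip, but less strongly than steps 1 and 2, because stopping for high pressure is not ruled out.

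**4. What the one-word correction changes.** After correction, *symptoms of* may govern both terms (reading A) or only the first (reading B).

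| Event in a short-acting nitrate user | As written | Corrected, A | Corrected, B |
|---|---|---|---|
| Symptomatic hypotension, including on standing | stop | stop | stop |
| SBP < 110 mmHg documented | stop | stop | stop |
| Postural rise | stop (under A, only with symptoms) | no stop | no stop |
| Postural fall without symptoms, SBP not below 110 mmHg | no stop | no stop | stop |

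Both readings remove the high-pressure trigger. Only B adds a new low-pressure case.

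**5. Can the documents choose between A and B?** No. Reading B is stricter than the reduce-first approach of 8.4.7.3, but 6.9 already departs from that approach: it stops drug for symptomatic hypotension, where 8.4.7.3 makes dose reduction the first step. A stricter rule for nitrate users is coherent, so 8.4.7.3 cannot decide the matter.

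**6. Effect on the analysis.** The sentence supplies no input to the sample size (Protocol 9.5, SAP 6.1), the alpha (Protocol 9.3, SAP 6.2.4) or the primary model (SAP 6.4.1.4). None of these changes.

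**The case against.** The strongest reply is that this is proofreading. Under reading A, the corrected rule stops drug for the same low-pressure events as now and removes only a trigger that nobody meant. Other protections exist: orthostatic hypotension is excluded at entry, the Investigator may interrupt drug at once, 7.1 allows stopping for any adverse event, and 2.3.1.3 has hypotensive episodes treated by standard of care. The study was completed under this amendment, so a correction now changes no conduct and no data.

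Most of that stands, and it is why the severity is low. It does not make the sentence right. A stopping rule that names the opposite condition is wrong as written, and the text may be reused.

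Two further replies also stand. First, the protocol does permit study drug to be stopped for severely elevated pressure, by discretion, so its handling of high pressure is supporting evidence only. Second, the visible text of 8.4.7.3 does not mention orthostatic falls, its thresholds are partly redacted, and detail may sit in the study reference manual. It therefore cannot be cited as covering a postural fall without symptoms.

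A reader might infer that the slip left a measurable safety gap, for example a range of standing falls in mmHg that went unprotected. The documents do not support this. Under reading A the correction adds no asymptomatic fall at all, and the sentence does not say whether the 110 mmHg limit is seated or standing. A reader might also infer that the rule was meant to stop drug for asymptomatic orthostatic hypotension, or that subjects were mismanaged. Neither is shown, and the number of nitrate users is not given.

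**Conclusion.** The point holds as a low-severity correction. One of the three triggers in an operative safety rule names the opposite of the condition almost certainly intended, and the intended one is missing. The conclusion rests on the low-pressure context of the sentence and the 5-to-1 use of terms, with the handling of high pressure as weaker support. *Almost certainly* is as far as the documents allow: neither contains a correction, and the memo to file described in SAP 1.2 concerns only Study Week versus Treatment Week. The practical effect is small, and there is none on sample size, alpha or the planned analyses. Whether asymptomatic orthostatic hypotension should stop study drug remains open and is for the sponsor to decide.

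**What to change.** In Protocol 6.9, replace *orthostatic hypertension* with *orthostatic hypotension*. In the same correction, state whether *symptoms of* applies to it:

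- If it does: stop for symptoms of hypotension or of orthostatic hypotension, or for a documented SBP below 110 mmHg.
- If it does not: stop for symptoms of hypotension, for orthostatic hypotension with or without symptoms, or for a documented SBP below 110 mmHg.

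Either is workable, and the choice is clinical. No new numeric criterion is needed. The correction can be made in a clarification memo, as was done on 06Aug2024 for the Study Week error (SAP 1.2), or in any later protocol that reuses the text. The documents do not show whether the open-label extension protocol does so; the sponsor can check. The cost is one word and a short phrase, with no change to data collection or analysis.
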